## 1.6 Rationale for Protocol Amendments

Four subjects were enrolled onto version 2 of the Phase 2 portion of the protocol. Three subjects (1 adult and 2 children) were administered 3e8 per wound daily for 5 days. One adult was administered 6e8 daily for 5 days. There were no signs of immunogenicity, no KB103-related adverse events and the data indicate that 3e8 per wound per administration was an effective dose for wounds 20 cm^2 or less.

Post-dose imaging from these patients clearly indicated that wound morphology and size is a major factor in wound healing as a result of KB103 administration. Wounds that were chronic but recurring based on natural history tended to heal and close completely within 7 to 10 days of KB103 administration. Chronic wounds that were open for a few years showed signs of healing following an initial five consecutive applications but the wound healing process appears to stagnate. These wounds would likely benefit from additional administrations to obtain full closure. Caregivers of the patients currently on trial have requested additional administrations to wounds that have clearly benefited but have not achieved complete wound closure.

Therefore, version 3.1 of the protocol incorporated dosing every 2 to 3 days for two weeks at 2e8 PFU with the option of at-home KB103 administrations, at the discretion of the Investigator.

Five patients were enrolled onto version 3.1 of the protocol. KB103 continues to be well tolerated and wound healing is observed in KB103 administered wounds. Wound healing results of the KB103 treated wounds evaluated to-date continues to show improvement. There is also empirical evidence that repeat administration on the chronic wounds that were retreated in patients that rolled over from the previous portion of the study showed improved healing with complete closure of the wound observed. Therefore, version 4.0 incorporates a 2-cycle approach to KB103 administration with greater flexibility given regarding the number of administrations within each cycle to understand the duration of treatment prior to moving into the Phase 3 Clinical trial.

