### 5.3.3 Screening and Baseline Procedures

The following procedures are performed on or the day before the first planned administration day.

- Review and signature of informed consent form
- The following evaluations are required only if RDEB diagnosis documentation is not available to support entry into this protocol. If these are needed, the screening visit may occur several weeks prior to the baseline visit:
  - Collection of a biopsy for EM/IEM
  - Collection of a biopsy for IF
  - Collection of blood for genetic testing
- Collection of demographic data (e.g. sex, age, race, and ethnicity)
- Inclusion/exclusion criteria
- Medical history and medication history
- Collection of blood (approximately 15 mL) for clinical laboratory tests:
  - Serum chemistry
  - Hematology
  - HIV, Hep B, Hep C
  - Baseline viral shedding
  - Baseline HSV and COLVII autoantibodies
- Collection of urine
  - For a pregnancy test, if applicable
  - For baseline viral shedding
- Physical and skin exam
- Vital signs: blood pressure, heart rate, respiratory rate, temperature
- Collection of a baseline skin swab for viral shedding analysis
- Bacterial culturing of target wounds (if clinical evaluation is indicative of infection)
- Digital imaging of target areas
- Collection of a biopsy from intact skin for IF and IEM analyses. This collection can occur at a later visit at the discretion of the Investigator.
- Patient reported outcomes (PRO) questionnaire
- Investigator's global assessment

## 5.4 Cycle 1

The patient will visit the Investigative site for the first dose of Cycle 1. Additional Cycle 1 doses can occur on-site or at-home at the discretion of the Investigator. Unless the patient requires disease characterization, Day 1 of Cycle 1 is the same day as the Screening/Baseline visit. For Cycle 1, KB103 and placebo are administered topically every 2 to 3 days to correspond with bandage changes, up to 3 months.

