#### 7.1.1 Imaging

Target wounds are measured at each visit to the clinic using a phone camera app. Investigators use the camera's software to define wound surface area and other measurements.

Target wounds are also monitored at home using the phone camera app. Subjects are instructed to image the target wounds during bandage changes (approximately twice per week).

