2.2 Study Objectives Phase II

2.2.1 Primary

- 8) To assess wound closure through post-administration imaging:
 - a. To assess proportion of complete wound closure of B-VEC treated wounds to that of placebo treated wounds at weeks 8, 10 and 12.
 - b. Time to wound closure of a KB103-administered wound relative to a placebo-administered wound
 - c. Duration of wound closure of a KB103-administered wound relative to a placebo-administered wound

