7.3 Treatment Compliance and Exposure

Exposure summary by treatment group will be presented for the Safety and PP populations. The distribution of subjects by the total number of weeks on therapy (baseline, 8, 10, and 12) will be presented. For the Safety population, the summary of exposure will be based on the actual treatment received.

Treatment compliance is defined as the number of wound treatment doses (KB103 and placebo) received divided by the number of doses expected, ($\times 100$) over the time period defined by the first and last treatment dose dates. Descriptive statistics for treatment compliance and the number and percentage of subjects at least 90% compliant will be presented by treatment group for the ITT, Safety, and PP populations.

8 Efficacy (Proof of Mechanism) Analyses

The study has a complete randomized-block design in which each subject serves as a block to receive all of the treatment conditions. The Phase I/II studies provided at least one pair of target wounds, with one wound being treated with placebo and one wound being treated with KB103. Efficacy measurements are taken multiple times (or repeatedly) over the on-treatment period and off-treatment period from each subject.

All data will be presented using summary statistics or frequency tables, as appropriate, and will be analyzed for superiority comparisons between KB103 and placebo treatments. The description of the sample will be done using summary statistics (n, mean, standard deviation, median, and maximum/minimum) for continuous data and using frequency statistics (counts and percentages) for categorical data. Hypothesis testing, unless otherwise indicated, will be performed at the 5% significance level (1-sided). All P-values will be rounded to four decimal places; P-values less than 0.0001 will be presented as '<0.0001' in all tables. Unless specifically stated, all confidence intervals will be two-sided with 95% coverage.

Efficacy measures collected pre-dosing will be considered as the baseline measurement (defined in [Section 6.2](#)) in this study. For all efficacy analyses, subjects will be analyzed in the group to which they were randomized.

The Sponsor, or their designee, will analyze the data using SAS® Statistical Analysis System Version 9.3 or higher.

8.1 Wound Efficacy Analyses:

8.1.1 Change in Wound Surface Area:

The efficacy analyses will be based on the observed ITT population.

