8.1.2 Time to Wound Closure

The time to wound closure defined as the time from the first treatment to complete wound closure ($\geq 90\%$ reduction in wound surface from baseline for 2 consecutive weeks) will be summarized by treatment and compared using analysis of variance with treatment as the fixed effect. This analysis will be performed for both Observed and LOCF imputed ITT populations

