8.1.3 Duration of Wound Closure

The duration of wound closure, defined as the time from the complete wound healing to the first reduction in wound surface from baseline to a value below 90%, will be summarized will be summarized by treatment and compared using analysis of variance with treatment as the fixed effect. This analysis will be performed for both Observed and LOCF imputed ITT populations

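### The models for time to closure and duration of closure name treatment only and leave out the subject block that defines the design

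*SAP*

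**What the plan says.** SAP 2.2.1 lists three Phase II primary items. The second is "Time to wound closure of a KB103-administered wound relative to a placebo-administered wound" and the third is "Duration of wound closure of a KB103-administered wound relative to a placebo-administered wound".

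The analysis of the second is in SAP 8.1.2: the times "will be summarized by treatment and compared using analysis of variance with treatment as the fixed effect". SAP 8.1.3 has durations "compared using analysis of variance with treatment as the fixed effect". The only variation in either section is observed versus LOCF-imputed data. No covariate or subject term appears, and no sensitivity analysis elsewhere in the SAP adds one for these endpoints.

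The opening of SAP section 8 describes the trial as a "complete randomized-block design in which each subject serves as a block", with testing at one-sided 5%.

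Baseline size is available. Protocol 5.3.3 lists "Digital imaging of target areas" at screening and baseline, and Protocol 7.1.1 has investigators use the camera's "software to define wound surface area and other measurements". Protocol 1.6 reports that "wound morphology and size is a major factor in wound healing as a result of KB103 administration".

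**The concern.** In a within-subject comparison, the gain in precision comes from removing what the wounds of one person share: genotype, age, general health, skin care. A model with treatment alone leaves that shared variation in the error term and computes the standard error as if all wounds came from different people. The estimate is then reported with the wrong uncertainty. In this layout, a positive within-subject correlation makes the test too strict and the interval too wide. With about 12 placebo wounds, that can hide a real difference.

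A smaller, related point is that starting wound size is measured but unused. Protocol 6.3 asks for similar wounds, but names only location on the body and only as far as possible. KB103 and placebo wounds in one subject can therefore differ in size.

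**Working it through.** The SAP gives no power, SD or correlation for these endpoints, so there is no figure of its own to reproduce.

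**Layout (SAP section 3 table; SAP 4.1).** Version 1.0: 2 subjects with 1 KB103 wound each. Versions 2.2 and 3.1: 4 + 5 = 9 subjects with 2 each. That is 2 + 18 = 20 KB103 wounds in 11 subjects. SAP 4.1 gives 12 subjects. I assume the twelfth is in version 4.0 with one KB103 area (Protocol 4.1 allows one or two). Totals: 21 KB103 and 12 placebo wounds; 3 subjects with one KB103 wound and 9 with two.

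**Assumed.** Total SD 1, true difference 0.8, within-subject correlation ρ of 0, 0.3 or 0.5, every wound closes, one-sided 5%.

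**1. True variance of the difference in means.** The 9 subjects with two KB103 wounds give 18 ordered pairs, and each KB103 wound shares a subject with one placebo wound:

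V = (21 + 18ρ)/441 + 1/12 − 2ρ/12

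The coefficient of ρ is 18/441 − 2/12 = 0.041 − 0.167 = −0.126, so positive correlation shrinks the true variance. At ρ = 0.5, V = 0.0680 + 0.0833 − 0.0833 = 0.0680 and SE = 0.261.

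**2. Variance the stated model reports.** This is s²(1/21 + 1/12) = 0.131 s², where the expected s² is [21 − (21 + 18ρ)/21 + 11]/31. At ρ = 0.5, s² = 30.57/31 = 0.986, so the reported variance is 0.129, nearly twice the true 0.068.

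**3. Consequence.** The critical value on 31 df is 1.696. On the true scale it becomes 1.696 × √(0.129/0.068) = 2.34.

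- Actual error ≈ 1 − Φ(2.34) = 1.0%. Simulations, which allow for variation in s², gave 1.4% and 2.2%.
- Power ≈ Φ(0.8/0.261 − 2.34) = Φ(0.73) = 77%.

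**4. With subject in the model (fixed block).** Information = 3 × (1/2) + 9 × (2/3) = 7.5, so the variance is (1 − ρ)/7.5 on 33 − 12 − 1 = 20 df, with critical value 1.725. At ρ = 0.5, SE = √(0.5/7.5) = 0.258 and the noncentrality is 0.8/0.258 = 3.10. Noncentral t power is 91%, with 5% error.

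| ρ | SE, true | Stated model: error | Stated model: power | With subject: power | Change |
|---|---|---|---|---|---|
| 0 | 0.362 | 5% | 70% | 68% | −2 |
| 0.3 | 0.305 | 2 to 3% | 73% | 81% | +7 to 8 |
| 0.5 | 0.261 | 1 to 2% | 77% | 91% | +14 |

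**5. Adding baseline area to the blocked model, ρ = 0.5.** Let r be the correlation of baseline area with the wound-level part of the outcome. The variance becomes (1 − ρ)(1 − r²)/7.5 × (1 + 1/18), the last factor allowing for chance imbalance, on 19 df.

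- r = 0.3: 0.0607 × 1.056 = 0.0640, noncentrality 3.16, power 92% (about +1).
- r = 0.5: 0.0500 × 1.056 = 0.0528, noncentrality 3.48, power 96% (about +5; a simulation gave 90.7% to 95.2%).

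**6. When many wounds do not close.** Simulation on closed wounds only, assuming 80% of KB103 and 33% of placebo wounds close and a true difference of 1.2 SD. It compares the stated model with a fixed subject block plus baseline area:

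| Both correlations | Stated model | Fixed block + area |
|---|---|---|
| 0 | 63% | 42% |
| 0.3 | 66% | 58% |
| 0.5 | 68% | 74% |

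Only about 12 × 0.33 = 4 subjects then have a closed placebo wound. A fixed block draws almost nothing from the rest.

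**The case against.** **The wording may imply a block.** SAP section 8 already states the block design, and naming treatment as the fixed effect does not rule out a random subject term. That is a possible reading. But SAP 8.1.2 and 8.1.3 name no other term, and a programmer following them would fit a one-way ANOVA. On either reading the text needs the term written in.

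**This is a pilot with no sample size calculation.** True, so no planned power is lost. A standard error that does not match the design is still wrong in a pilot, and these are primary objectives.

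**Blocking can cost power.** This stands in part. If all correlations are near zero, or if few placebo wounds close and subject is a fixed effect, the blocked model can be worse, as step 6 shows. This argues for a random subject effect, which also uses subjects with closed wounds in one arm only.

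**A stronger reading on baseline area.** A reader might infer that omitting wound area by itself costs 9 to 10 points of power. That comes from treating 33 wounds as independent and assuming both a starting power and r = 0.5 (80% becomes 88.9%, 70% becomes 80.5%). The documents supply neither figure, and with the trial's clustering the gain is 1 to 5 points. The supporting text is also weaker than it looks:

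- Protocol 1.6 names morphology together with size, and illustrates the statement by how long wounds had been open.
- The rise in the cap from 10 to 20 to 50 cm² does not show that spread of wound size. In version 4.0 the 50 cm² is a skin area that may include intact skin (Protocol 6.3). Caps also differ between versions, hence between subjects, which a subject term largely absorbs.
- Closure is a percentage reduction from each wound's own baseline, so the endpoint is already partly scaled for size.

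**Conclusion.** The concern holds for the subject block. As written, the models for two of three Phase II primary objectives ignore the structure that SAP section 8 says defines the design. If wounds in one person are positively correlated, the test is conservative and loses power; nothing here suggests an inflated false-positive rate. At an assumed correlation of 0.5, the actual error is 1 to 2% instead of 5%, and power is about 77% instead of 91%.

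These figures rest on the assumed layout, a 0.8 SD difference, approximately normal outcomes and every wound closing. None of the correlations comes from the documents. Baseline area is a useful but secondary addition. How wounds that never close or never reopen enter the analysis is a separate question, but the answer affects how the subject term should be fitted.

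**What to change.** In SAP 8.1.2 and 8.1.3, replace the treatment-only ANOVA with a linear mixed model:

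- Fixed effects: treatment and log baseline wound area of the target wound, using the SAP 6.2 baseline. For version 4.0, specify the open wound surface, not the treated skin area.
- Random effect: subject, as the block, with a small-sample degrees-of-freedom method such as Kenward-Roger.
- Report the adjusted difference with its interval, and keep the unadjusted comparison as a sensitivity analysis.
- If a time-to-event model is adopted for wounds that do not close, carry the subject term into it as a shared frailty or as clustering.
- Avoid a fixed subject block if many placebo wounds may never close.

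The cost is SAP wording and a few lines of code, with no new data. The covariate uses one degree of freedom, and a little power is lost if both correlations are near zero. SAP section 1 says a partial analysis has already been done on unblinded data, so the model terms should be fixed in writing before the complete analysis.

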8.1.3 Duration of Wound Closure

The duration of wound closure, defined as the time from the complete wound healing to the first reduction in wound surface from baseline to a value below 90%, will be summarized will be summarized by treatment and compared using analysis of variance with treatment as the fixed effect. This analysis will be performed for both Observed and LOCF imputed ITT populations

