### **7.3 Investigator's Global Assessment Score**

Areas administered topical KB103 and placebo will be clinically evaluated at baseline and at Days 15, 30, 45, 60, 90, and unscheduled visits with an IGA score of: 1) complete closure (i.e., 100% healed), 2) <100% to 75% healed, 3) 74% to 50% healed, 4) 49% to 0% healed, 5) unable to determine, or 6) not assessed. The IGA score is used to provide a snapshot of overall disease severity in dermatologic clinical studies, (Langley, et al., 2015) including EB (Tabolli, et al., 2009). Results to date in a Phase 1/2a keratinocyte graft study suggest that wound measurements from imaging and IGA score are supportive and well correlated (Dutt-Singkh, et al., 2018).

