### 10.5.3 Target Wound Area

Target wound surface area is obtained through on-site and at-home imaging of target areas. Change in area from baseline is evaluated for using a paired t-test for each KB103 target wound vs. control wound.

Time to closure and durability of closure will be assessed after each cycle of administrations.

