6.1 General Conventions

The following general comments apply to all statistical analyses and data presentations:

- Summaries will include frequency and percentages for categorical data; frequency and median for ordinal data; and frequency, mean, standard deviation, and median, minimum, and maximum for quantitative data.
- Duration variables will be calculated using the general formula (end date – start date) +1.
- Change from baseline will be calculated for each subject at the specified time point as the value at the specified time point minus the baseline value.
- Individual subject listings of all data represented on the eCRFs will be provided to facilitate the investigation of tabulated values and to allow for the clinical review of all efficacy and safety parameters.
- Version 9.1.3 (or higher) of SAS® statistical software package will be used to provide all summaries, listings, graphs, and statistical analyses.

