6.3 Handling of Missing Data

Missing data will be handled as outlined below:

- All missing and partial dates for adverse events or for medications received after randomization will be queried for a value. If no value can be obtained, substitutions will be made as detailed in [Appendix 2](#). These substitutions will be used in calculations; however, the actual value recorded on the eCRF will be used in all listings.
- Missing primary endpoints, values after the last non-missing value would be replaced by the last recorded observed value. This is analogous to a last observation carried forward (LOCF) strategy for study discontinuations. For all the other endpoints, the missing values will not be imputed.
- The severity and causality assessment for adverse events cannot be missing. Missing data will be queried for a value.

7 Statistical Analysis Methods

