The efficacy objective is the proportion of DEB wound sites with complete wound healing from baseline ($\geq 90\%$ reduction in wound surface from baseline) in KB103 versus placebo treated intra-participant wound sites at Weeks 8, 10 and 12 as determined by the Investigator.

The number and percentage of subjects in each treatment group defined as Complete Wound Healing (CWH) will be tabulated. The null and alternative hypotheses are as follows:

Null Hypothesis $H_0: \%CWH \text{ in KB103} = \%CWH \text{ in Placebo}$

Alternate Hypothesis $H_1: \%CWH \text{ in KB103} > \%CWH \text{ in Placebo}$

Where $\%CWH$ is the percentage of wounds with a complete wound healing from baseline at week 8, 10 and 12. A one-sided significance level of 0.05 is considered

The objective of the proportion of DEB wound sites with complete wound healing from baseline ($\geq 90\%$ reduction in wound surface from baseline) will be analyzed using the Cochran-Mantel-Haenszel (CMH) test stratified by the time points (weeks 8, 10 and 12). Under the null hypothesis of no association between complete wound healing and treatment, this test statistic follows a chi-square distribution with 1 degree of freedom. The CMH test provides test of independence for the repeated evaluations at weeks 8, 10 and 12.

In addition to testing the null hypothesis, the CMH test also provides an estimate of the common odds ratio to summarize how large the treatment effect is when pooled across the different weeks of the treatment assuming the odds ratio is the same in the different weeks of treatment. This assumption will be tested using the Breslow-Day test and corresponding p-values will be provided. The null hypothesis of the CMH test is that the odds ratios within each week are equal to 1, indicating the complete wound healing proportions are the same.

A summary table with individual treatment proportions and the p-values treatment effect resulting from the chi-square test will be provided. In addition, p-values for independence of weekly evaluations (weeks 8, 10 and 12) using the Breslow-Day test will be provided.

8.1.1.1 Sensitivity and Supplemental Analyses of the Change in Wound Surface Area:

- The analysis performed in Section 8.1.1 for the efficacy objective will be repeated for the PP and LOCF imputed ITT populations.

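### SAP 8.1.3 compares duration of wound closure by ANOVA but gives no end date or censoring rule for wounds still closed at their last assessment

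*SAP*

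**What the plan says.** SAP 8.1.3 starts the clock at complete healing and stops it at the "time from the complete wound healing to the first reduction in wound surface from baseline to a value below 90" percent. The result is "compared using analysis of variance with treatment as the fixed effect", on observed and on LOCF-imputed ITT data.

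SAP 2.2.1 lists "Duration of wound closure of a KB103-administered wound relative to a placebo-administered wound" among the Phase II primary objectives, and protocol 2.1 has the same item as 1c. In Phase I, duration of healing is a secondary objective (SAP 2.1.2). The SAP analyses both phases.

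Three other rules bear on the calculation:

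- SAP 6.1: "Duration variables will be calculated using the general formula" of end date minus start date, plus one.
- SAP 6.3: "Missing primary endpoints, values after the last non-missing value would be replaced by the last recorded observed value".
- Protocol 10.7: the last measurement serves as the treatment endpoint, and nothing else is imputed.

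On cycles, protocol 10.5.3 says "Time to closure and durability of closure will be assessed after each cycle of administrations". SAP 8.1.3 does not mention cycles.

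**The concern.** The SAP 6.1 formula needs an end date for every wound. A wound that never falls below a 90% reduction during follow-up has none, and these are the wounds that stayed closed longest under observation. ANOVA has no means of using a duration known only to exceed some value. The analyst therefore has to make a choice that the SAP does not state, and the two obvious choices give different answers.

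The silence carries extra weight here because the SAP introduction says that the plan was written after a partial analysis of an unblinded study. The choice could be made with results in view, for an objective that is primary in Phase II.

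**Working it through.** The documents give no sample size, effect size or re-opening time for this endpoint, so there is no figure of the plan's own to reproduce.

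**Step 1: does any rule supply the missing end date?** SAP 8.1.3 ends closure only below 90%. LOCF under SAP 6.3 carries a closed wound's area forward, so the wound stays closed and still has no re-opening date. Protocol 10.7 takes the last measurement as the endpoint value, which likewise is not a re-opening. No other section of either document has a censoring rule. The gap is present in both the observed and the LOCF analysis.

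**Step 2: can it arise?** The last fixed visit is Day 84 in version 1.0, Day 90 in versions 2.2 and 3.1, and three months after Cycle 2 in version 4.0 (SAP Appendix 1). Protocol 1.6 reports that recurring wounds tended to close within 7 to 10 days. Taking closure on Day 10, a wound still closed on Day 90 has 90 − 10 + 1 = 81 observed days and no end.

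**Step 3: how many wounds are exposed?** From the table in SAP section 3, versions 1.0 to 3.2 planned:

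- KB103: 2×1 + 4×2 + 5×2 = 20 wounds
- placebo: 2 + 4 + 5 = 11 wounds

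**Step 4: what does the unstated choice do?** Pair that 81-day wound with one that re-opens after *a* days (assumed values).

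| *a* (days) | Mean if closed wound dropped: *a* | Mean if last visit is the end: (*a* + 81)/2 | Gap |
|---|---|---|---|
| 10 | 10 | 45.5 | 35.5 |
| 30 | 30 | 55.5 | 25.5 |
| 60 | 60 | 70.5 | 10.5 |

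**Step 5: what does it do to a treatment comparison?** This is an illustrative simulation with 4,000 runs per scenario. It uses 22 KB103 and 12 placebo wounds: the counts above plus a twelfth subject assumed to have two KB103 areas and one placebo area. Also assumed: exponential durations, every wound closes, wounds independent, re-opening dated exactly, and follow-up to Day 90. Tests are two-sided at 0.05, because the ANOVA F test has no direction.

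No true difference in duration, with KB103 wounds closing on Days 7–28 and placebo wounds on Days 28–70. The table shows how often each method rejects:

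| Median in both arms (days) | ANOVA, last visit as end | ANOVA, still-closed dropped | Log-rank with censoring |
|---|---|---|---|
| 30 | 16% | 13% | 5.1% |
| 60 | 51% | 11% | 5.0% |
| 120 | 86% | 8% | 4.6% |

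The spurious mean difference in favor of KB103 is 9.4, 17.0 and 22.9 days with the last visit as the end, and 8.9, 11.8 and 12.7 days with still-closed wounds dropped.

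If both arms close on Days 7–28 and there is no true difference, all three methods reject in 4.4% to 6.1% of runs.

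With equal closing times and true medians of 120 and 30 days, the true mean difference is (120 − 30)/ln 2 = 130 days. ANOVA shows 7 days if closed wounds are dropped and 24 if the last visit is used. Power is 10% and 76%, against 84% for log-rank.

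**Step 6: cycles.** Only version 4.0 has cycles. It planned 3 subjects. SAP section 3 reports 12 patients treated to date, and 2 + 4 + 5 = 11 belong to the earlier versions, which leaves 1 by subtraction.

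**The case against.** The best defense is that this is a pilot with no formal sample size, that SAP 6.1 and 8.1.1.1 already promise listings, and that every number in steps 4 and 5 rests on assumed durations. False rejections appear in the simulation only when the arms close at different times. Nor does SAP 8.1.3 say whether closure starts at the first 90% reading or after the two consecutive weeks used in SAP 8.1.2, so the 81-day example is itself one reading.

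All of this limits the size that can be claimed. It does not supply an end date. The SAP chose a treatment comparison for this endpoint, under a general 5% one-sided testing rule, and different closing times are what an effective treatment would be expected to produce.

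A reader might infer something stronger about dosing: that the endpoint is undefined because a wound can be dosed while it counts as closed. The mismatch exists. A 20 cm² wound re-opened to 1.5 cm² has a reduction of 1 − 1.5/20 = 92.5%. It counts as closed in the SAP, yet it is visibly open and may be dosed under protocol 6.4. But SAP 8.1.3 gives a definite answer: closure ends at the first value below 90%, whatever the dosing. The objective is duration of closure, not duration off treatment.

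Making a re-dose end closure would also be unfair between arms. Only re-opening in a KB103 area starts Cycle 2 (protocol 4.1), and placebo follows KB103 dosing days (protocol 6.5), so a KB103 wound would be scored as re-opened while an identical placebo wound was not.

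Nor is re-dosing confined to version 4.0. Version 1.0 re-doses a wound that was closed at Day 28 and re-opens by Day 42, and version 2.2 lists doses on Days 30, 60 and 90.

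**Conclusion.** The concern holds for the missing end date. As written, the SAP 8.1.3 comparison cannot be computed for any wound still at a 90% or greater reduction at its last assessment, and both obvious workarounds bias the durations. Dropping such wounds removes the longest observed closures. Using the last visit as the end favors whichever arm closes earlier, and also shrinks a true difference.

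This applies to every protocol version, for an objective that is primary in Phase II and secondary in Phase I. The size in this trial is unknown. The simulation shows mechanism and direction under stated assumptions, not an expected error rate.

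The absent cycle split is a real mismatch between protocol and SAP, but it carries little numerical weight. The documents do not support going further and calling the whole endpoint undefined or the result impossible to interpret. The change should be made.

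**What to change.** In SAP 8.1.3:

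- Keep the 90% definition, identically for both arms.
- Censor each wound that has not fallen below 90% at its last assessment.
- Replace ANOVA with Kaplan-Meier curves by treatment, noting that wounds within a subject are related.
- Add a per-wound listing of closure date, re-opening or censoring date, and dosing dates. For all protocol versions, show days closed during dosing separately from days closed after the last dose, without changing the end point.
- Report version 4.0 by cycle, as protocol 10.5.3 requires.

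The cost is a few lines of SAP text and one derived listing, built from image dates, wound areas and dosing dates. No visit or measurement is added, and the protocol needs no edit.

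There are downsides. Some durations become censored, so the summary is less precise, and a listing alone gives no p-value. Kaplan-Meier cannot show closure beyond the last visit, and it still compares only wounds that closed.
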